### 11.3.3 **Progression free Survival**

**Progression-Free Survival:** Progression-Free Survival (PFS) is defined as the time from registration to the earlier of progression or death due to any cause. Participants alive without disease progression are censored at date of last disease evaluation.

**Overall Survival:** Overall Survival (OS) is defined as the time registration to death due to any cause, or censored at date last known alive.

### 11.3.4 **Central Radiology Interpretation**

All scans will be reviewed centrally by the Tumor Imaging Metrics Core (TIMC) either by submission through their secure portal, or by mailing de-identified (only including subject number, trial number, date of scan, timepoint, and site contact information).

Radiographic responses will then be communicated to the investigative sites for entry in to the EDC.

**Scans will be uploaded to the secure file transfer portal at:**  
<https://transfer.partners.org/courier/web/1000@/wmLogin.html>

#### **External Site Access:**

External collaborators must be invited to use the system. Please email the study lead if a new staff member needs access to this portal.

1. If you used the old system, type in your email address, click Next, then select the "forgot password" link to reset your password
2. If you're new, please ask your MGB collaborator to send you an email from <https://transferkw.partners.org>
3. Email Tumor Imaging Metrics Core help desk ([[contact]](mailto:[contact])) and provide two email addresses for account registration (a primary and a backup)
4. TIMC will send an invite via the Partners Healthcare Secure File Sharing service
5. Click the link in the email to accept the invitation and register your account
  - a. *Invitations will expire after 7 days*
  - b. Check Spam and Junk email folders for invite if not received in Inbox
6. Create a password
7. Click Register

#### **Send Files**

1. Create a desktop folder
2. Copy DICOM data from CD into the desktop folder

CONFIDENTIAL

This document is confidential. Do not disclose or use except as authorized.

- a. Remove any image viewers as this will interfere with data upload to the local analysis software
3. Right click folder > Send To > Compressed (zipped) folder
1. Log in to the system: <https://transferkw.partners.org>
4. Select Send File tab
5. Enter [[contact]](mailto:[contact]) into the To field
6. Enter a subject into the Subject field
7. Select Choose File > browse the desktop for the zipped file
8. Add patient initials, trial number, and any notes pertaining to the scan or assessment in the body of the email
  - a. Do not include any protected health information (PHI) in the email subject line
9. Select notification preferences from the Additional Options field (optional)
10. Click 'Mark as secure (fingerprint)'
11. Click Send
12. Click OK after receiving confirmation that the files have been sent
- 13. Notify the lead site PM that a file has been uploaded, so that an order can be placed for the scan to be read.**

## **12. DATA REPORTING / REGULATORY REQUIREMENTS**

Adverse event lists, guidelines, and instructions for AE reporting can be found in Section 7.0 (Adverse Events: List and Reporting Requirements).

### **12.1 Data Reporting**

#### **12.1.1 Method**

The Office of Data Quality (ODQ) will collect, manage, and perform quality checks on the data for this study.

#### **12.1.2 Responsibility for Data Submission**

Investigative sites within DF/HCC or DF/PCC are responsible for submitting data and/or data forms to the Office of Data Quality in accordance with DF/HCC SOPs.

### **12.2 Data Safety Monitoring**

The DF/HCC Data and Safety Monitoring Committee (DSMC) will review and monitor toxicity and accrual data from this study. The committee is composed of clinical specialists with experience in oncology and who have no direct relationship with the study. Information that raises any questions about participant safety will be addressed with the Overall PI and study team.

CONFIDENTIAL

This document is confidential. Do not disclose or use except as authorized.

The DSMC will review each protocol up to four times a year or more often if required to review toxicity and accrual data. Information to be provided to the committee may include: up-to-date participant accrual; current dose level information; DLT information; all grade 2 or higher unexpected adverse events that have been reported; summary of all deaths occurring with 30 days of intervention for Phase I or II protocols; for gene therapy protocols, summary of all deaths while being treated and during active follow-up; any response information; audit results, and a summary provided by the study team. Other information (e.g. scans, laboratory values) will be provided upon request.

### **12.3 Multicenter Guidelines:**

This protocol will adhere to the policies and requirements of the DF/HCC Multi-Center Data and Safety Monitoring Plan. The specific responsibilities of the Overall PI, Coordinating Center, and Participating Institutions and the procedures for auditing are presented in Appendix B.

- The Overall PI/Coordinating Center is responsible for distributing all IND Action Letters or Safety Reports to all participating institutions for submission to their individual IRBs for action as required.
- Mechanisms will be in place to ensure quality assurance, protocol compliance, and adverse event reporting at each site.
- Except in very unusual circumstances, each participating institution will order the study agent(s) directly from supplier. A participating site may order the agent(s) only after the initial IRB approval for the site has been forwarded to the Coordinating Center.

### **12.4 Collaborative Agreements Language: N/A**

CONFIDENTIAL

This document is confidential. Do not disclose or use except as authorized.

### 13. STATISTICAL CONSIDERATIONS

#### 13.1 Study Design/Endpoints

##### *Phase I Study: Evaluation of Toxicity*

**Primary Endpoint:** The primary endpoint in the phase I study is the dose limiting toxicity (DLT), and the maximum tolerated dose (MTD) as well as the recommended phase II dose for this combination regimen of duvelisib plus venetoclax.

A standard 3+3 dose escalation design will be employed with three dose levels of venetoclax. Patients will be treated in cohorts of size three to six and the dosage will be escalated if the clinical toxicity is acceptable. A dose-limiting toxicity (DLT) is defined as per section 5.3, and the DLT observation period is the first cycle of combination treatment.

The design is constructed to reduce the chance of escalating the dose when the probability of DLT is high, and increase the chance of escalating the dose when the probability of DLT is low. The maximum tolerated dose (MTD) is defined as the highest dose level where a DLT occurs within at most one out of six patients treated. The escalation scheme is as follows:

- (1) If none of the initial three patients in a cohort experiences a DLT, then a new cohort of three patients will be treated at the next higher dose level.
- (2) If one of the three patients in a cohort experiences a DLT, then up to three additional patients will be treated at the same dose. Escalation will continue if only one of the six patients experiences DLT.
- (3) If two or more patients in a cohort experience DLT, then the MTD will have been exceeded, and no further dose escalation will occur. The previous dose level will be considered the MTD.
- (4) If only three patients were treated at a dose level under consideration as the MTD, then up to three additional patients will be accrued. If no more than one of the six patients at that dose level experience a DLT, then that dose level will be confirmed as the MTD. If two or more patients in that cohort experience DLT, then the previous dose level will be studied in the same fashion.

The MTD is defined as the highest dose studied for which the observed incidence of DLT is less than 33%. Frequencies of toxicities will be tabulated according to the NCI Common Toxicity Criteria. Patients will be continued to be followed for one year for evidence of late toxicity.

**Table 10: Below gives the probabilities of dose escalation based on true DLT risk in the 3+3 design.**

True DLT rate:	10%	20%	30%	40%	50%	60%	70%	80%	90%
Probability of	0.91	0.71	0.49	0.31	0.17	0.08	0.03	0.01	0.001

CONFIDENTIAL

This document is confidential. Do not disclose or use except as authorized.

escalation									
------------	--	--	--	--	--	--	--	--	--

In the phase I study, if a patient comes off study due to a reason other than a DLT (e.g. disease progression) prior to the end of the DLT observation period, that patient can be replaced.

***Phase II Study (CLL/SLL patients):***

***Treatment Efficacy***

The primary endpoint for the phase II study is the rate of complete response (CR) at 12 months according to 2008 IW-CLL criteria. The CR rate will be obtained for all patients at 12 months and will be reported as a percentage of total patients.

***Evaluation of Toxicity in Phase II***

We will closely monitor treatment-related toxicity for all participants. Participants in the phase II portion of the study who meet DLT criteria during the first cycle of combination treatment as specified in section 5.3 will be analyzed by the following method:

Sequential Pocock-type stopping boundaries will be used to monitor the unexpected toxicity rate (Ivanova et al., 2005). Accrual will be halted and the Data Safety Monitoring Committee consulted if excessive numbers of unexpected toxicities are seen, that is, if the number of toxicities is equal to or exceeds  $b_n$  out of  $n$  patients who received at least one dose of combination therapy (see table 11). For example, if 6 or more out of the first 20 patients ( $\geq 40\%$ ) experience unacceptable toxicities the study will be stopped; or if 8 or more out of the first 30 patients ( $\geq 26\%$ ) experience unacceptable toxicities the study will be stopped. With these rules, the probability of early stopping the trial if the true rate of toxicity is  $\leq 10\%$  does not exceed 0.05, if the true toxicity rate is 30% the probability of early stopping is 0.865 (table 12).

Table 11: The trial will be stopped if the number of toxicities is equal to or exceeds  $b_n$  out of  $n$  patients evaluable for toxicity.

Number of Patients, $n$	Boundary, $b_n$
1	-
2	2
3	3
4	3
5	3
6	3
7	4
8	4
9	4
10	4
11	5
12	5
13	5
14	5
15	5
16	6
17	6
18	6
19	6
20	6
21	6
22	7
23	7
24	7
25	7
26	7
27	7
28	8
29	8
30	8
31	8
32	8
33	8
34	9
35	9

Table 12: Probabilities of early stopping at different true but unobserved toxicity rates.

Toxicity Rate	0.10	0.20	0.30	0.40	0.50	0.60
Probability of early stopping	0.048	0.436	0.865	0.988	0.999	1.00

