## **5.1 Treatment Regimen**

### **5.1.1 Duvelisib:**

Duvelisib will be administered twice daily, with 28 consecutive days defined as a treatment cycle (up to 49 days for cycle 1), for up to a total of 12 cycles. Treatment will be administered on an outpatient basis with the exception of doses given while inpatient for venetoclax ramp up/dose escalation. Appropriate dose modifications are described in Section 6. Reported adverse events and potential risks are described in Section 7. No investigational or commercial agents or therapies other than those described below may be administered with the intent to treat the participant's malignancy.

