### 5.3 Definition of Dose-Limiting Toxicity (DLT)

Dose-limiting toxicity (DLT) is based on the CTEP Active Version of the NCI Common Terminology Criteria for Adverse Events (CTCAE) Version 5.0. DLT refers to toxicities experienced at any time during the first cycle of study treatment, defined as the following:

- Grade 4 neutropenia lasting more than 5 days
- Febrile neutropenia of any duration ( $ANC < 1.0 \times 10^9/L$  and fever  $\geq 38.5^\circ F$ )
- Grade  $\geq 3$  thrombocytopenia with clinically significant bleeding
- Grade  $\geq 4$  infection by NCI-CTCAE criteria
- Any grade 3 or greater non-hematologic toxicity with the following exceptions:
  - Grade 3 or greater nausea/vomiting/diarrhea that persists for 7 days or less
  - Grade 3 asymptomatic laboratory abnormalities that improve to grade 2 or less within 3 days
- Any grade  $\geq 3$  diarrhea or vomiting or diarrhea that requires tube feeding, total parenteral nutrition, or requires or prolongs hospitalization
- Inability to receive Day 1 therapy of Cycle 2 after a delay in treatment of up to 21 days due to continued drug related toxicity from the prior cycle
- Severe cutaneous reaction (grade 3 or greater)
- Grade 4 elevation in ALT and/or AST or grade  $\geq 3$  elevation in ALT and/or AST occurring in the context of a Grade  $\geq 2$  elevation in bilirubin
- Grade 5 treatment-related adverse events

All toxicities will be considered relevant to determining DLTs and to reporting unless the event can clearly be determined to be unrelated to the study drug(s).

The DLT observation period is considered the period from the first dose of combination therapy through the completion of cycle 1. In the phase I study, if a patient comes off study due to a reason other than a DLT (e.g. disease progression) prior to the end of the DLT observation period, that patient can be replaced.

CONFIDENTIAL

This document is confidential. Do not disclose or use except as authorized.

Management and dose modifications associated with the above adverse events are outlined in Section 6.

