## **11. MEASUREMENT OF EFFECT**

### **11.1 Definitions:**

Evaluable for toxicity: All participants who receive at least one dose of study treatment will be evaluable for toxicity from the time of their first treatment.

Evaluable for DLT: All participants who complete the first cycle of combination therapy will be evaluable for DLT from the time of their first treatment. Any patient who experiences a DLT after receiving at least one dose of combination study treatment will also be considered evaluable for DLT. In the phase I portion of the study, if a patient comes off study due to a reason other than a DLT (e.g. disease progression) prior to the end of the DLT observation period, that patient can be replaced.

Evaluable for objective response: Only those participants who have measurable disease present at baseline, have received at least one cycle of therapy, and have had their disease re-evaluated will be considered evaluable for response. These participants will have their response classified according to the definitions stated below. (Note: Participants who exhibit objective disease progression or die prior to the end of cycle 1 will also be considered evaluable.)

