#### **13.4.1 Evaluation of Toxicity**

All participants who receive at least one dose of combination therapy (duvelisib and venetoclax) will be evaluable for toxicity from the time of their first treatment.

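### The phase II toxicity rule counts patients whose cycle 1 outcome is still pending, so it can halt later and somewhat less often than Table 12 implies; a check in dosing order removes the avoidable part

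*Combined protocol and SAP*

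**What the plan says.** Under Evaluation of Toxicity in Phase II (section 13.1), the monitored events are those of participants "who meet DLT criteria during the first cycle of combination treatment as specified in section 5.3". Accrual is halted and the DSMC consulted when the count reaches b_n out of n "patients who received at least one dose of combination therapy (see table 11".

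The caption of Table 11 reads "The trial will be stopped if the number of toxicities is equal to or exceeds" b_n, with n described as those evaluable for toxicity. Section 13.4.1 gives that term the same meaning: "All participants who receive at least one dose of combination therapy (duvelisib and venetoclax) will be evaluable for toxicity". The caption and the governing sentence therefore agree that n grows at the first combination dose.

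The event takes longer to establish. Section 5.3 states: "The DLT observation period is considered the period from the first dose of combination therapy through the completion of cycle 1". Section 5.1.1 allows "up to 49 days for cycle 1", and venetoclax starts on day 8.

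Section 11.1 has a different definition, "All participants who complete the first cycle of combination therapy will be evaluable for DLT", which also admits anyone who has already had a DLT. The stopping rule does not use it. The worked example in 13.1 speaks of the first 20 and the first 30 patients. Section 13.2 names accrual rate in its title but gives none. Nothing is said about staggering patients or handling those still pending.

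**The concern.** The denominator moves on the first day of the window and the numerator fills over the following weeks. Under Table 11, three DLTs in six patients is a halt (b_6 = 3). If a seventh patient is dosed before the third DLT is recorded, the rule compares 3 with b_7 = 4 and accrual continues. With 11 dosed it needs 5. Patients about whom little is yet known have then overridden a signal among earlier patients.

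This rule is the phase II cohort's only numerical safety boundary. If it works more slowly than Table 12 suggests, more patients are treated with a regimen that is too toxic, and the DSMC relies on operating characteristics that belong to a different procedure.

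**Working it through.** **Inputs.** Boundary from Table 11: none at n = 1; 2 at n = 2; 3 at 3–6; 4 at 7–10; 5 at 11–15; 6 at 16–21; 7 at 22–27; 8 at 28–33; 9 at 34–35. Maximum n = 35 (13.2). Window: days 8 to 49, so 49 − 7 = 42 days at most. A 20 mg start gives five weekly steps, about 35 days. Accrual: not stated; 1 to 4 per month assumed.

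**Step 1: reproduce Table 12.** Let f_n(k) be the probability of k DLTs after n patients with no crossing so far:

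- f_n(k) = f_{n−1}(k)(1 − p) + f_{n−1}(k − 1)p, for k < b_n
- P(first crossing at n) = f_{n−1}(b_n − 1)p

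Summing over n = 1 to 35, with each outcome known before the next patient is counted:

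| True rate p | 0.10 | 0.20 | 0.30 | 0.40 |
|---|---|---|---|---|
| Table 12 | 0.048 | 0.436 | 0.865 | 0.988 |
| Recursion | 0.049 | 0.438 | 0.866 | 0.988 |

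The published figures match a calculation with no pending patients. At p = 0.30 the same recursion gives 16.6 patients treated on average, 0.409 for a halt before the 12th patient, and 0.861 for a crossing before the 35th is dosed.

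**Step 2: a fixed number pending, exact.** If L patients are always pending and DLTs are known only at the end of the window, events among the first m patients face b_{m+L} (capped at b_35). At p = 0.30 the probability of ever crossing is 0.844 (L = 1), 0.827 (L = 2), 0.800 (L = 4) and 0.774 (L = 8). The floor is P(X ≥ 9) = 0.766 for X binomial(35, 0.30). The average number pending is about rate × 42/30.4: 1.4 at 1 per month, 2.8 at 2 and 5.5 at 4.

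**Step 3: simulation.** Poisson accrual, 42-day window, DLT time uniform over the window, p = 0.30. Ranges span repeated runs with and without a one-year gap after patient 12, which makes little difference.

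| Accrual per month | 1 | 2 | 4 |
|---|---|---|---|
| **n = all dosed (as written)** | | | |
| Ever crosses | 0.853–0.857 | 0.841–0.845 | 0.822–0.829 |
| Halt before 12th patient | 0.35–0.36 | 0.30 | 0.19–0.21 |
| Mean treated | 17.8–18.0 | 19.2–19.3 | 21.2–21.7 |
| **b_n applied in dosing order** | | | |
| Ever crosses | about 0.865 | about 0.865 | about 0.865 |
| Halt before 12th patient | 0.40 | 0.37 | 0.30–0.32 |
| Mean treated | 17.1–17.3 | 17.8–17.9 | 18.8–19.3 |
| Crosses before 35th dosed | 0.856 | 0.848 | 0.831 |

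Difference in mean treated, in the runs without the gap: 18.0 − 17.2 = 0.8; 19.3 − 17.9 = 1.4; 21.7 − 19.2 = 2.5. In runs with the gap, 17.8 − 17.1 = 0.7 at 1 per month.

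At p = 0.10, false stops are 0.042, 0.035 and 0.026 as written, and about 0.05 (exact 0.049) in dosing order.

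**Step 4: the other obvious repair.** Counting only patients who are evaluable for DLT under 11.1 admits events sooner than non-events. At p = 0.10, false stops rise to 0.059, 0.077 and 0.110 at 1, 2 and 4 per month, above the plan's limit of 0.05.

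**The case against.** The worked example can be read as enrolment order. On that reading a later pending patient cannot cancel an earlier crossing, and the eventual stopping probability stays at 0.865. This stands as evidence of what may have been intended. However, the governing sentence and 13.4.1 do not say it, and a halting rule should not depend on which reading is chosen.

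The loss in eventual stopping is small at slow accrual: about 1 point at 1 per month and about 4 at 4 per month. The documents do not establish the fast end. The only accrual figure, in 19.3, is a recommended phase I minimum of 2 per site per year. Going from 6 to 11 dosed within one window would need 5/42 × 30.4 = 3.6 per month. A 20 mg start also shortens the window to about 35 days. All of this stands, and limits the size of the effect.

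The rule is not the sole safeguard. Sections 5.3.1 and 12.2 have the DSMC reviewing toxicity up to four times a year, and 12.2 adds more often if required. That softens the consequence but does not mend the rule.

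Two stronger inferences are not supported. A reader might infer that newly dosed patients cannot yet have an event; 5.3 puts them at risk from the first combination dose, so they are only partly observed. A reader might also blame the denominator for the whole delay. At 4 per month, mean treated rises from 16.6 to 19.2 even in dosing order (2.6 patients), and the denominator adds 2.5. Roughly half is therefore unavoidable.

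**Conclusion.** The point holds as a defect in how n is defined. As written, partly observed patients raise the boundary, and Table 12 describes a procedure without them. At a 30% true rate and an assumed 1 to 4 patients per month, eventual stopping is about 0.85 to 0.83 instead of 0.865. The chance of a halt before the 12th patient is about 0.35 to 0.19, where dosing order would give 0.40 to 0.31. The denominator costs about 0.7 to 2.5 extra patients on average. Timing matters more than the final probability.

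These sizes rest on the assumed accrual, a 42-day window and DLTs spread evenly over it. If DLTs come at the end of the window, eventual stopping is lower: 0.843, 0.826 and 0.808 at 1, 2 and 3 per month. It cannot fall below 0.766.

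It would go too far to conclude that the stated 0.865 is unattainable, since the enrolment-order reading delivers it as a probability of ever crossing. It would also go too far to say that reading restores Table 12 as a probability of stopping accrual early: crossing before the 35th patient is dosed is then about 0.86 to 0.83.

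**What to change.** Replace the sentence defining n with: *At each new DLT, order patients by first combination dose; halt accrual if, for any n up to the number dosed, DLTs among the first n patients are at least b_n.* Table 11 stays as it is and the worked example then fits the rule.

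Label Table 12 as the probability of ever crossing, and state the accrual rate assumed, so that the DSMC can see how much delay remains.

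Do not simply switch n to the 11.1 evaluable-for-DLT count, for the reason in the last step of the working.

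The cost is one sentence and one table label, with no extra patients or data. False stops return from 0.042–0.026 to about 0.05, the level the plan already accepts.

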***Phase II Study (Richter’s Syndrome Cohort):***

In a previous study with a commonly used chemoimmunotherapy regimen for RS, dose-adjusted EPOCH-R, the CR rate was 20%. We base this as the null hypothesis. With the addition of

CONFIDENTIAL

This document is confidential. Do not disclose or use except as authorized.

venetoclax, we hypothesize that the CR rate will be 45% or higher. Twenty patients will be enrolled and if 7 or more patients achieve CR we will regard the treatment efficacious. Conversely, if 6 or fewer patients achieve CR, we will regard the treatment inefficacious. With this design, the probability of concluding the treatment efficacious is 0.87 if the true but unknown response rate is 45% and 0.09 if the true rate is 20%. This decision rule is calculated using the exact binomial method. Table 1 below shows the operating characteristics of this design.

Table 1. Operating Characteristics

	True but Unknown CR Rate					
	20%	25%	30%	35%	40%	45%
Prob( $\geq 7$ CR in 20)	0.09	0.21	0.39	0.58	0.75	0.87

